### Participant timeline

TIMEPOINT	STUDY PERIOD			
	Enrolment	Allocation	Post-allocation	
	Day -1	Day 0	Day 2	Day 7
ENROLMENT:	Urine specimen received at microbiology laboratory	Urine culture result reported to physician	Physician treatment decision made	Safety assessment
Eligibility screen	X			
Allocation		X		
INTERVENTIONS:				
Reporting		X		
ASSESSMENTS:				
Appropriateness			X	
Adverse Events			X	X
Bacteremia			X	X
Mortality			X	X

## **Sample size**

In the previous trial of the same intervention, modified reporting increased the appropriateness of treatment from 29/55 (52.7%) to 44/55 (80.0%) ( $p=0.002$ ), for an absolute difference of +23%. Accepting a risk of type 1 error of five percent, and a risk of type 2 error of twenty percent, the study will require  $2N=90$  patients. To account for missing data, recruitment will be increased to 100 patients.

The microbiology laboratory receives 130 urine specimens per day, with 30 percent reported as significant growth (40 specimens per day). Twenty-five percent are submitted from inpatients (10 specimens per day). Approximately 33% of inpatient urines are collected from catheters, however collection method is not always provided to the laboratory. This leaves approximately three urine specimens per day which may be eligible for inclusion. In the previous trial, approximately 40% of eligible specimens were excluded based on exclusion criteria. Recruitment of 100 specimens will require approximately 60-90 days.

The statistical test to be used is a comparison of proportions between two groups (T test, two-sided analysis). Because true diagnosis may be biased by lack of access to clinical information, an intention to treat analysis including all patients randomized will be performed.

## **Recruitment**

Every urine specimen received for culture during the study period will be assessed for inclusion.

## **Allocation:**

## **Sequence generation**

Randomization sequence will be generated without blocking or stratification (Research Randomizer 4.0).

### **Allocation concealment**

Reporting assignments will be placed into serially numbered, sealed, opaque envelopes.

### **Implementation**

Allocation sequence will be generated by investigators. Investigators will enroll specimens and assign specimens to reporting interventions.

### **Blinding**

Trial participants (physicians) will not be blinded to the intervention because the laboratory report will reveal the intervention. One investigator will serve as outcome assessor, and will be blinded to assignment. Data analyst will not be blinded to assignment.

### **Data collection methods**

After randomization and reporting, a blinded physician investigator will assess inpatients for the true diagnosis of CA-ASB or CA-UTI at two days after reporting. Health records will be accessed including demographics, symptoms, treatment decisions and outcomes (treated CA-ASB, treated CA-UTI, untreated CA-ASB, untreated CA-UTI).

If patients are discharged from hospital before seven days, primary care physicians will be contacted by phone for additional clinical information. If patients die before seven days, available data will be analyzed.

Frequency of physician calls requesting complete reporting will be recorded.

Urine culture is reported according to laboratory protocol by licenced medical laboratory technologists, in categories of significant growth, non-significant growth, and no growth, based on quantity of growth and number of bacterial types detected. Antimicrobial susceptibility is reported according to laboratory protocol, including selected first and second-line antibiotics, as susceptible, intermediate or resistant. Drug cost and dosage suggestion are provided.

Data collection form attached.

### **Data management**

Data will be entered into the trial dataset by a single investigator. Data collection will use a paper case report form, and entered into a trial database by a single investigator. Variables will be coded appropriately. The dataset will be protected using a password and stored on a laptop computer during data entry. After data entry is completed, data integrity will be reviewed by a second investigator, and then the dataset will be locked for analysis.

### **Statistical methods**

All specimens randomised and reported will be included in the Intention-to-treat (ITT) analysis. Specimens inappropriately included will be excluded from the Per-protocol (PP) analysis. The proportion of appropriate treatment will be compared using two-sided Pearson chi squared test (SPSS 23.0, IBM, USA). Adjusted analysis will not be performed. A subgroup defined as specimens in which physicians requested complete reporting will be analysed for appropriateness, compared to the standard reporting arm. Missing data will not be imputed.

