A randomized, unblinded controlled trial was performed in St. John's, among patients without indwelling catheters, using the same intervention.(11) Results of positive urine cultures from 110 consecutive inpatients at two urban acute care hospitals were randomised to standard report or modified report. Specimens randomized to the modified report were reported as follows: “This POSITIVE urine culture may represent asymptomatic bacteriuria or urinary tract

infection. If urinary tract infection is suspected clinically, please call the microbiology laboratory for identification and susceptibility results.”

Exclusion criteria were age less than 18 years, pregnancy, presence of an indwelling urinary catheter, samples from patients already on antibiotics, neutropenia, or admission to an Intensive Care Unit. Patients were followed for seven days, and physician treatment decisions were observed. 76/110 (69%) of positive urine cultures represented ASB. The proportion of appropriate treatment (UTI treated plus ASB not treated) was higher in the modified arm than in the standard arm (44/55 (80.0%) vs 29/55 (52.7%), absolute difference=-27.3%, RR=0.42, p=0.002, Number needed to report for benefit=3.7).

There were two bacteremias in the modified report group, and one bacteremia in the standard report group, none of which were considered related to the intervention. There were two deaths in the modified report group, and one death in the standard report group, none of which were considered related to the intervention. Based on this trial, the intervention was considered safe over 7 days of followup, and effective to reduce inappropriate treatment, but further study would be required among populations excluded from the trial.

We propose to repeat the trial using an identical design and intervention, but including only urine collected from indwelling catheters. The control arm is standard of care. We hypothesize that the modified reporting intervention will also demonstrate effectiveness at reducing treatment of ASB in this population, without causing harm.

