### **Methods: Participants, interventions, and outcomes**

The proposed study is a randomized trial of two methods of laboratory reporting in which physicians are the main research participants. At the time of positive urine culture results, the specimen will be randomized by computer generated random number placed into serially numbered sealed, opaque envelopes, into two equal groups. One group will receive modified reporting, and the other group will receive standard reporting of identification and susceptibility. Physicians will then have the option of calling the laboratory to receive the results or not. Complete results will be released by telephone and laboratory information system to physicians who call to request them. Physicians will be informed about the study prior to initiation, and debriefed about the study after the results have been collected.

The definition of CA-UTI will be based on the Infectious Diseases Society of America guidelines,(2) not the Centers for Disease Control National Health Safety Network surveillance definition, which is not designed for clinical care.(12) The definitions to be used in patients with indwelling urethral, indwelling suprapubic, or intermittent catheterization are as follows:

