#### CA-ASB

1. presence of  $\geq 10^5$  cfu/mL of  $\geq 1$  bacterial species in a single catheter urine specimen in a patient without symptoms compatible with UTI.

Signs and symptoms compatible with CA-UTI include new onset or worsening of fever, rigors, altered mental status, malaise, or lethargy with no other identified cause; flank pain; costovertebral angle tenderness; acute hematuria; pelvic discomfort; and in those whose catheters have been removed, dysuria, urgent or frequent urination, or suprapubic pain or tenderness. In patients with spinal cord injury, increased spasticity, autonomic dysreflexia, or sense of unease are also compatible with CA-UTI.

The primary efficacy outcome is proportion of appropriate antibiotic therapy prescribed by physicians, based on published diagnostic criteria for ASB and UTI among catheterized patients. Appropriate therapy is defined as any treatment for UTI, or no treatment for ASB. The primary safety outcome is rate of bacteremia and death.

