### **Interventions**

The modified report states "This POSITIVE urine culture may represent asymptomatic bacteriuria or urinary tract infection. If urinary tract infection is suspected clinically, please call the microbiology laboratory at [name] between 0900 to 2300, or the microbiology technologist on-call at [name] at night, for identification and susceptibility results." The standard report provides bacterial count, bacterial identification and bacterial susceptibility results.

The report is provided to the physician approximately 24 hours after receipt of the specimen, when cultures have been examined after overnight incubation. The intervention is a single report, so it is not possible to discontinue the intervention, or change allocation during the trial. There will no other influence on concomitant care or treatment.

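### Comparing modified-report specimens whose physician called with the whole standard arm selects on a post-randomisation choice, and can show a large difference in either direction when the report has no effect

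*Combined protocol and SAP*

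**What the plan says.** The Statistical methods section first defines the intention-to-treat and per-protocol analyses and the two-sided Pearson chi-squared test. It then adds: "A subgroup defined as specimens in which physicians requested complete reporting will be analysed for appropriateness, compared to the standard reporting arm". The same section states "Adjusted analysis will not be performed".

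Three other places determine what this subgroup is:

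- **When the call happens.** The opening Methods section, describing events after allocation, says: "Physicians will then have the option of calling the laboratory to receive the results or not".
- **Why the call happens, and in which arm.** The modified report in the Interventions section reads in part: "If urinary tract infection is suspected clinically, please call the microbiology laboratory". In the other arm no call is needed: "The standard report provides bacterial count, bacterial identification and bacterial susceptibility results".
- **What the outcome is.** Under the CA-ASB definition: "Appropriate therapy is defined as any treatment for UTI, or no treatment for ASB".

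The documents do not say what the subgroup is for, do not label it exploratory and do not limit its interpretation. They give no expected call rate; the proportion of calls appears only as a secondary outcome.

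**The concern.** The two groups compared are not the groups that were randomised. One is the part of the modified arm whose physicians chose to call. The other is the entire standard arm, which has no identifiable counterpart of specimens whose physician would have called.

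The selection also acts directly on the outcome. A physician who calls is likely to suspect UTI, to be inclined to treat, or both. Appropriateness is determined by exactly those two things, true diagnosis and treatment. If callers hold more true UTI than the standard arm, they tend to look more appropriate. If they hold more treated ASB, they look less appropriate. Neither result requires the report to have changed a single decision.

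At stake is the interpretation of the mechanism. A positive difference invites the reading that calling leads to appropriate treatment, and a negative one that calling leads to overtreatment. Either could be drawn falsely, in a trial whose Implications section looks to adoption in routine laboratory practice.

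**Working it through.** **Benchmark.** The plan gives no figure for the subgroup, so I take the planned effect as the scale. The Sample size section cites 29/55 = 52.7% and 44/55 = 80.0%, a difference of 27.3 points. (The section prints +23%, but its own proportions give 27.3.) With these proportions, two-sided alpha 0.05 and 80% power, the unpooled formula gives n = (1.960 + 0.842)² × (0.527×0.473 + 0.800×0.200) / 0.273² = 43.2. That rounds up to 44 per arm, or 2N = 88. The pooled formula gives 46 per arm, or 2N = 92. The stated 90 lies between them, so 27.3 points is the effect the trial is sized for.

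**Inputs.** From the previous trial in the Background, "76/110 (69%) of positive urine cultures represented ASB". Hence ASB = 76/110 and UTI = 34/110. Appropriate treatment under standard reporting was 29/55 = 58/110. These come from non-catheterised patients and serve as illustration. Two things are assumed and varied: the share of UTIs treated, tU (80% to 100%), and the calling pattern.

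**Null model.** The report changes no treatment decision, so both whole arms have 52.7% appropriate and the true difference is 0. The share of ASB treated, tA, follows from

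UTI × tU + ASB × (1 − tA) = 29/55,

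which gives tA = 0.684, 0.639 and 0.595 for tU = 1.0, 0.9 and 0.8. With tU = 1.0, every 110 specimens contain 34 treated UTI, 52 treated ASB and 24 untreated ASB.

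**Appropriateness among callers** = (called treated UTI + called untreated ASB) / all called. With tU = 1.0:

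- Callers are exactly those who treat: 34/(34 + 52) = 39.5%, so 39.5 − 52.7 = −13.2 points.
- Calls for true UTI only: 34/34 = 100%, so +47.3 points.
- Calls for 90% of UTI, 20% of treated ASB, 5% of untreated ASB: (30.6 + 1.2)/(30.6 + 10.4 + 1.2) = 31.8/42.2 = 75.4%, so +22.6 points.
- Calls for 80%, 50% and 10% respectively: (27.2 + 2.4)/(27.2 + 26 + 2.4) = 29.6/55.6 = 53.2%, so +0.5 points.
- Calls for 30%, 80% and 5% respectively: (10.2 + 1.2)/(10.2 + 41.6 + 1.2) = 11.4/53 = 21.5%, so −31.2 points.

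**Full range.** Each cell gives the expected false difference in percentage points. In brackets is the share of 200,000 simulated trials in which a two-sided 5% chi-squared test rejects, comparing 50 standard specimens with the callers among 50 modified specimens.

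| Who calls (UTI / treated ASB / untreated ASB) | tU = 100% | tU = 90% | tU = 80% |
|---|---|---|---|
| Unrelated to either (50% of all) | 0 (5.3%) | 0 (5.4%) | 0 (5.3%) |
| True UTI only | +47.3 (99.9%) | +37.3 (81.8%) | +27.3 (48.7%) |
| 90 / 20 / 5% | +22.6 (40.5%) | +16.6 (23.2%) | +10.5 (12.0%) |
| 80 / 50 / 10% | +0.5 (5.4%) | −2.5 (5.8%) | −5.8 (8.0%) |
| Exactly those treated | −13.2 (23.9%) | −14.1 (25.5%) | −15.2 (27.5%) |
| 30 / 80 / 5% | −31.2 (74.8%) | −31.8 (75.3%) | −32.5 (75.4%) |

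The true effect is zero in every cell. Sign and size depend only on who calls and on how many UTIs are treated.

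**The case against.** The case on the other side is mainly about size and weight.

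- **The +47 is an extreme corner.** It needs every UTI treated and called about, while 68.4% of ASB is treated without anyone asking for identification or susceptibility. This stands. The figure is an upper bound, and with 80% of UTIs treated the same pattern gives +27.3.
- **Some patterns give no bias.** Also true, as the table shows. But the documents give no call rates, and the comparison itself cannot show which pattern occurred, so a near-zero bias could not be recognised.
- **The selection mechanism is inferred.** Any physician who calls is given the results, whatever the reason. That is so, but the report invites calls on suspicion of UTI, and bias is absent only if calling is unrelated to diagnosis and treatment or the two influences happen to cancel.
- **The rates come from patients without catheters.** This stands. They set the scale of the illustration; the argument does not rest on them.
- **The ban on adjustment matters little.** Agreed. Adjusting for diagnosis would not remove selection on the decision to treat, so lifting the ban would not rescue the contrast.
- **The analysis is supplementary.** Agreed. It is not listed under Outcomes, and it does not touch the primary comparison, the sample size or the interim stopping rule. No test is named for it specifically, so a descriptive comparison may be meant. A descriptive contrast with the wrong comparator is biased in the same way.

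These points limit the consequence. None makes the comparison valid.

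**Conclusion.** The concern holds. The planned contrast sets a self-selected part of one arm against the whole of the other, with selection acting on the components of the outcome. With no effect of the report, the expected difference ranges from about −32 to +47 points over the calling patterns examined, including values near zero, against a planned effect of 27.3 points. If the report does have an effect, the contrast mixes that effect with selection and cannot separate them.

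The sizes rest on the previous trial's case mix and standard-arm rate, on 80% to 100% of UTIs being treated, and on assumed calling patterns. The design flaw rests on none of these; it follows from the definitions in the plan. I read the subgroup as modified-arm callers, because only that arm needs a call. If calls about standard-arm specimens were counted, the subgroup would overlap its own comparator.

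**What to change.** In Statistical methods, remove the clause that names the standard arm as comparator and replace the sentence with wording such as:

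*Within the modified-report arm, specimens will be tabulated by whether the physician called, by diagnosis (CA-UTI or CA-ASB) and by treatment (treated or untreated). Counts and proportions will be presented without a hypothesis test. Callers will not be compared with the standard-report arm.*

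Between-arm comparisons then stay with the groups as randomised, plus the per-protocol set already defined. The report should add that differences between callers and non-callers within the arm also reflect who chose to call.

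The cost is one sentence. The Data collection methods section already provides for recording calls and all four diagnosis-by-treatment outcomes. Calls must be linked to specimens, but the existing subgroup needs that too. No further patients or variables are required, and the primary analysis is unchanged.

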### **Data monitoring**

A data monitoring committee will not be used, as a single investigator will assume responsibility for data quality. A single interim analysis at approximately 50% recruitment will be performed, and the study stopped if the primary outcome achieves statistical significance.

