## **Objectives**

Research Question: Among inpatients with positive urine cultures collected from indwelling catheters reported by Health Sciences microbiology laboratory, would restricted

reporting, as compared to standard reporting, lead to a reduction in the rate of inappropriate antibiotic therapy without an increase in bacteremia or death?

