### **Outcomes**

Primary efficacy outcome:

Proportion of appropriate antibiotic therapy prescribed by physicians. Appropriateness is determined by investigators based on chart review, based on diagnosis of CA-UTI or CA-ASB.

Appropriateness is determined within seven days from positive urine culture.

Secondary efficacy outcomes:

Proportion of calls from physicians requesting complete report

Primary safety outcomes:

Mortality rate over seven days from positive urine culture.

Bacteremia rate over seven days from positive urine culture.

Adverse event rate over seven days from positive urine culture.

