### **Harms**

Serious adverse events will be reported to the ethics committee within 24 hours. Adverse events will be collected by the investigators at day 2 and day 7. Patients with adverse events will be provided care in hospital.

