### **Research ethics approval**

The protocol will be submitted to the Provincial Health Research Ethics Board.

Physician consent requirement will be requested to be waived because the intervention poses no more than minimal risk to participants. Patient consent requirement will be requested to be waived because physicians were the research subjects. A letter will be sent to all inpatient physicians informing them about the study prior to recruitment, and a debrief meeting, offering an opportunity to withdraw physician participation, will be provided.

The benefit of this study to patients includes a reduction in adverse events caused by inappropriate antibiotic treatment. The risk to patients includes possible untreated CA-UTI. The benefit to physicians includes education toward appropriate treatment of CA-ASB. The risk to physicians includes additional effort to access laboratory results for CA-UTI.

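### The one interim look acts only on the primary outcome, and the plan provides no by-arm comparison of deaths and bacteremias, its primary safety outcome, while enrolment is open

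*Combined protocol and SAP*

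**What the plan says.** The Data monitoring section has two sentences. The first is "A data monitoring committee will not be used, as a single investigator will assume responsibility for data quality". The second is "A single interim analysis at approximately 50% recruitment will be performed, and the study stopped if the primary outcome achieves statistical significance".

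The outcome definitions, at the end of the CA-ASB section, separate efficacy from safety: "The primary efficacy outcome is proportion of appropriate antibiotic therapy prescribed by physicians", and "The primary safety outcome is rate of bacteremia and death". The Outcomes section sets a seven-day window, for example "Bacteremia rate over seven days from positive urine culture". The Objectives make safety part of the question: would restricted reporting "lead to a reduction in the rate of inappropriate antibiotic therapy without an increase in bacteremia or death"?

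Safety reporting is in the Harms section: "Serious adverse events will be reported to the ethics committee within 24 hours". Adverse events are collected by the investigators at day 2 and day 7. The section mentions no comparison between arms and does not say what follows from a report. The Auditing section rules out auditing.

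Under Research ethics approval, waivers of physician and patient consent are to be requested, and the plan acknowledges that "The risk to patients includes possible untreated CA-UTI".

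**The concern.** The reason given for having no committee, responsibility for data quality, does not bear on what such a committee would do for patient safety. The only planned look during enrolment examines whether antibiotic treatment was appropriate. The safety reports that do flow are single cases.

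Single cases are a weak basis for judgement here. Deaths and bacteremias occur in inpatients for unrelated reasons, and every such event in the earlier trial was judged unrelated to the intervention (Background and rationale). A modest excess in one arm shows up only when the arms are set side by side with their denominators, and the plan does not provide for this before the end.

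The plan names untreated infection as a patient risk and seeks consent waivers. The earlier trial excluded catheterised patients and called for further study in excluded populations. If safety is first compared at the end, the second half of the patients is enrolled without information that the investigators already hold.

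**Working it through.** **1. Provisions set side by side**

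| Safeguard | Runs during enrolment? | Compares arms on death or bacteremia? | Stated consequence |
|---|---|---|---|
| Interim look (Data monitoring) | Yes, once, at about 50% | No; primary outcome only | Stop if significant |
| Serious adverse event reports (Harms) | Yes, within 24 hours | Not stated | Not stated |
| Adverse event collection, days 2 and 7 (Harms) | Yes | Not stated | Not stated |
| Committee, auditing | None | – | – |

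The only test that Statistical methods specifies is a two-sided Pearson chi-squared test on appropriateness of treatment. No section gives a test, margin or review rule for safety.

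**2. Inputs**

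- Size at the look: recruitment target 100 (Sample size), equal allocation (Trial design), 50% look, so 100 × 0.5 / 2 = 25 per arm if the split is even. The plan states no safety figure to reproduce. Its stated size of 90 concerns efficacy and is close to the 92 (46 per arm) that 52.7% vs 80.0% gives at two-sided 5% and 80% power.
- Event rates: the documents give none for catheterised patients. The earlier trial, in non-catheterised patients, had 1 death and 1 bacteremia among 55 standard-arm patients, and 2 and 2 among 55 modified-arm patients. Taking each event as a different patient (assumption): standard arm 2/55 = 3.6%, both arms pooled 6/110 = 5.5%. Rates of 10%, 15% and 20% are assumptions, used to show the range.

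**3. What a by-arm table could show**

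Let M ~ Bin(25, p_M) and S ~ Bin(25, p_S) be the numbers of patients with death or bacteremia in the modified and standard arms. As a yardstick only, take a lead of three:

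P(M − S ≥ 3) = Σ P(M = a) P(S = b) over all a − b ≥ 3.

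| True rate, standard | True rate, modified | P(lead ≥ 3) |
|---|---|---|
| 3.6% | 3.6% | 2.9% |
| 5.5% | 5.5% | 5.6% |
| 10% | 10% | 11.5% |
| 15% | 15% | 16% |
| 3.6% | 7.3% (4/55) | 15% |
| 3.6% | 10% | 29% |
| 3.6% | 15% | 56% |
| 3.6% | 20% | 76% |

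The first four rows are false alarms and the last four are true excesses.

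**4. Unequal arms**

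Sequence generation specifies no blocking. With 50 patients allocated by simple randomisation, a split of 30/20 or worse in either direction has probability 2 × P(Bin(50, 0.5) ≤ 20) = 2 × 0.101 = 20%. With 30 modified and 20 standard, the false-alarm chance of a raw lead of three becomes 5.4% at a 3.6% rate, 10.7% at 5.5% and 23% at 10%. A raw count difference is therefore a poor trigger, and any threshold should use proportions.

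**5. Follow-up at the look**

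Recruiting 100 in 60 to 90 days means that 7 × 100/90 = 7.8 to 7 × 100/60 = 11.7 patients enter in any seven days. If the table is made as soon as the fiftieth patient is enrolled, about 8 to 12 will not have completed safety follow-up.

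**The case against.** Several points on the other side stand. The plan does have safety oversight: serious adverse events reach the ethics committee within 24 hours throughout recruitment, and nothing says that the committee cannot act. The modified report itself states that the culture is positive and gives day and night contacts, and full results are released to any physician who calls. Pregnant, neutropenic and intensive-care patients are excluded. The trial is small and short, so doing without a full committee is a defensible design choice.

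A reader might infer that nothing in the plan can pause the trial, so that it must run on while harm builds up. The text does not support that. It leaves the by-arm comparison unstated; it does not bar the ethics committee or the investigators from acting. Nor does silence prove that nobody will look, since the data analyst is unblinded (Blinding) and the investigators collect the adverse events. A reader might also take data quality as the reason for having no safety oversight; it is given only as the reason for having no committee. Consent is not yet waived: waivers are to be requested, although the Consent or assent section reads not applicable.

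It could also be argued that the primary outcome in the stopping rule includes the primary safety outcome. Even so, the planned test would be a blunt instrument. At 25 per arm, 4 vs 0 gives a pooled rate of 4/50 = 0.08 and z = 0.16 / √(0.08 × 0.92 × 2/25) = 2.09 (p = 0.037), whereas 3 vs 0 gives z = 1.79 (p = 0.074). With one or two standard-arm events, significance needs 6 vs 1 or 8 vs 2. At true rates of 3.6% vs 15% to 20%, that test would be significant against the modified arm in about 27% to 47% of trials.

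What remains is that no safeguard in the plan is stated to compare the arms on the primary safety outcome while enrolment is open.

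**Conclusion.** The gap is real but limited. It lies in what the trial does, not only in its wording: followed as written, about 50 of 100 patients are enrolled after an interim look that leaves out the primary safety outcome, unless the trial stops for efficacy. The ethics committee receives case reports but is not stated to receive a comparison.

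The documents do not show that harm is expected. The earlier trial's counts (2 vs 1 bacteremias, 2 vs 1 deaths) neither show it nor rule it out.

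A table at the look would reveal only large excesses: a lead of three in 29% of trials at 3.6% vs 10%, and in 56% to 76% at 3.6% vs 15% to 20%. These figures assume an even split, each event in a different patient, complete follow-up, and a standard-arm rate borrowed from non-catheterised patients. They do not support a particular trigger: the false-alarm chance of that lead runs from about 3% to 16% over the assumed rates, and higher when the modified arm is the larger. The change is worth making because it is cheap and concerns patient safety; a full committee is not required.

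**What to change.** Add to Data monitoring that, at the planned interim look, the unblinded data analyst, and not the blinded outcome assessor, tabulates by arm the patients with death or bacteremia within seven days. The table gives the number randomised in each arm and the number who have completed seven days. It goes to the ethics committee, which decides whether enrolment continues.

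Any numeric threshold for a pause should be set in advance by the investigators and the ethics board, on proportions and not raw counts because randomisation is unblocked. No value is proposed here. Also give a reason for having no monitoring committee that rests on safety, such as the trial's size and duration together with the ethics committee's role.

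The cost is a short paragraph and one table from data already collected at days 2 and 7, with no new committee. The downside is a possible short, unnecessary pause. Its probability depends on the threshold chosen and on the event rate in catheterised patients, which the investigators would need to supply. A single look will still miss modest excesses and any that arise after it, so the 24-hour reports remain necessary.

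### The only interim stopping rule appears to rest on the efficacy outcome, so an early stop could leave the safety part of the question with about half its planned data

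*Combined protocol and SAP*

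**What the plan says.** The Data monitoring section declines a data monitoring committee and sets one interim look with one rule: "A single interim analysis at approximately 50% recruitment will be performed, and the study stopped if the primary outcome achieves statistical significance". It gives no significance level for that look, no safety criterion, no minimum number of patients for safety, and no continuation for safety after efficacy is shown.

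The Objectives ask whether modified reporting reduces inappropriate therapy "without an increase in bacteremia or death". The Outcomes section lists mortality, adverse events and "Bacteremia rate over seven days from positive urine culture" as primary safety outcomes, and the Implications section makes adoption conditional on the intervention being judged safe. Under Research ethics approval the plan acknowledges: "The risk to patients includes possible untreated CA-UTI".

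Statistical methods names a test, the two-sided Pearson chi-squared, for the proportion of appropriate treatment only. The Harms section has adverse events collected at day 2 and day 7 and serious events sent to the ethics committee within 24 hours. It does not call for a comparison between arms.

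**The concern.** The trial asks a two-part question, but the rule that can end it early reads most naturally as looking at one part. Significance on appropriateness at the halfway look would stop the trial at roughly 22 to 25 patients per arm, whatever the deaths and bacteremias show and however few patients inform them. No section assigns anyone to compare those events by arm at that point.

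The earlier trial of this report excluded patients with indwelling catheters, so this trial would be the first randomised safety information that the documents describe for them. That trial had 55 per arm. A stop here would leave less than half of that.

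**Working it through.** **Inputs.** Appropriate treatment was 29/55 = 52.7% and 44/55 = 80.0% (Sample size). Error rates come from the same section: "Accepting a risk of type 1 error of five percent, and a risk of type 2 error of twenty percent". The sample size is 2N = 90, with recruitment raised to 100. Allocation is equal (Trial design) and unblocked (Sequence generation). Half of 90 to 100 is 45 to 50 specimens, or about 22 to 25 per arm. The interim level is not stated; nominal two-sided 5% is assumed.

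**Step 1: reproduce the plan's sample size.** With mean proportion p̄ = 0.664 and d = 0.273, the pooled formula is

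n = [1.96·√(2p̄(1−p̄)) + 0.842·√(p₁(1−p₁) + p₂(1−p₂))]² / d² = 45.9, so 46 per arm and 2N = 92.

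The unpooled formula gives 44 per arm, 2N = 88. The plan's 90 lies between them. The Sample size section also prints "for an absolute difference of +23" per cent. That conflicts with 80.0 − 52.7 = 27.3 and with the Background, which has "absolute difference=-27.3%, RR=0.42, p=0.002". A 23-point difference needs 2N = 136 (52.7% versus 75.7%) or 126 (57% versus 80%), so 52.7% versus 80.0% is the pair behind the 90.

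**Step 2: chance of stopping at the interim.** For arm size n, sum the product of the two binomial probabilities over all outcomes where the uncorrected Pearson statistic reaches the critical value (3.84 at 5%).

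| Assumption | 22 per arm | 23 per arm | 25 per arm |
|---|---|---|---|
| 52.7% v 80.0%, level 0.05 | 47.8% | 50.5% | 56.0% |
| 52.7% v 75.7%, level 0.05 | 34.6% | 37.1% | 42.2% |
| 57% v 80%, level 0.05 | 36.9% | 39.1% | 43.5% |
| 52.7% v 80.0%, Pocock-type 0.0294 | – | 42.3% | 44.4% |
| 52.7% v 80.0%, O'Brien-Fleming-type 0.0054 | – | 19.6% | 21.8% |

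Allowing for unblocked randomisation, the first row becomes 49.5% at 45 specimens and 54.3% at 50.

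**Step 3: what is lost for safety.** With zero events in an arm, the upper limit of the exact two-sided 95% interval is 1 − 0.025^(1/n):
- n = 25: 13.7%
- n = 50: 7.1%

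With one event in each arm, the Newcombe 95% interval for the difference is ±√[(p−l)² + (u−p)²], where l and u are the Wilson limits:
- n = 25: p = 0.04, l = 0.0071, u = 0.1954, giving ±15.9 points
- n = 50: p = 0.02, l = 0.0035, u = 0.1050, giving ±8.7 points

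**Step 4: how exact is half?** Recruiting 100 in 60–90 days is 1.1 to 1.7 specimens a day. Waiting 2 to 7 days for outcomes without pausing adds about 2 to 12 specimens, so the safety set could reach about 62, or 31 per arm.

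**Step 5: the second efficacy test.** Two looks at nominal 5%, at half and full information (correlation √0.5 = 0.707), give an overall type I error of 1 − P(|Z₁| < 1.96, |Z₂| < 1.96) ≈ 8.3%.

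**The case against.** The strongest reply is that the full trial cannot settle safety either. At 50 per arm, if the earlier trial's bacteremia rates carried over (1/55 versus 2/55), the chi-squared test would have about 5% power. Against a fourfold rate (1/55 versus 4/55) it would have about 23%. This stands: the early stop worsens an existing limitation, and completing recruitment does not remove it.

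A second reply is that the size depends on choices the plan does not make. This also stands. The 48–56% needs a nominal 5% level and the 27.3-point difference; an O'Brien-Fleming-type boundary brings it to about 20–22%. A reader might infer that an even chance of stopping follows directly from the plan's own assumptions. It does not, because no interim level is stated and the Sample size section contradicts itself on the difference.

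Third, a reader might infer that efficacy is already settled and safety is the only new question. The documents do not support that. The earlier trial excluded catheterised patients, this trial is designed for superiority, and its size rests on appropriateness alone. Efficacy is also untested in this population.

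Finally, the interim rule does not explicitly exclude safety. It says primary outcome without qualification, and it fixes only the trigger for stopping, not everything the interim may examine. Efficacy remains the natural reading because safety has no stated test, but the wording needs clarifying in either case.

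**Conclusion.** The point holds as a design weakness that should be corrected. As most naturally read, the interim rule can end the trial on efficacy with about half the planned safety data, and no other section requires a by-arm safety look or a minimum safety sample.

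The chance of this is about 48–56% at 22–25 per arm under an assumed nominal 5% level and 52.7% versus 80.0%. It is about 37–44% at 23–25 per arm with the printed 23-point difference. With the 27.3-point difference and an adjusted boundary it is about 42–44% (Pocock-type) or 20–22% (O'Brien-Fleming-type). A stricter boundary therefore reduces the risk but does not remove it. The consequence is roughly a doubling of safety uncertainty. Half is approximate, since specimens enrolled while outcomes are pending would add a few patients.

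It would go too far to say that the rule decides whether safety is answered, or that the plan has no safety oversight. Serious events do go to the ethics committee; what is missing is a planned comparison between arms.

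**What to change.** In Data monitoring, remove the early stop for efficacy, so that the planned 100 specimens are completed and all contribute to the safety outcomes. This also removes the unadjusted second efficacy test. Keep the look at about 50% recruitment, but use it to tabulate deaths, bacteremias and adverse events by arm, and give that table to the ethics committee that already receives serious events. The data analyst, who is unblinded under the Blinding section, can prepare it; the blinded outcome assessor should not see it.

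The cost is one protocol sentence and one table from data already collected, with no patients beyond the plan. The ethics committee would need to agree to receive comparative data, and the table carries no stopping criterion of its own. The real downside is losing the option to save about 30–45 days, half of the 60–90 days planned for recruitment.

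If the sponsor prefers to keep an efficacy stop, the section should at least name the outcome, state the interim level and set a minimum safety sample. In either case, correct the 23-point figure in Sample size to agree with 52.7% and 80.0%.
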